# 3.7.1.4 Analyses of pharmacokinetic/pharmacodynamic

Efficacy endpoints for PK/PD analysis include response status, tumor shrinkage (eg, best relative tumor shrinkage or best tumor shrinkage). The relationship between those endpoints and PK will be assessed through descriptive statistics and plots.

The relationship between response status and the prognostic PK parameters may be analyzed by fitting a logistic regression model if a sufficient number of responses is observed. Moreover, if relevant, the relationship between best relative tumor shrinkage and the prognostic PK parameters may be analyzed by fitting a linear regression model.

# 3.7.2 Subgroup analyses

To assess the homogeneity of the treatment effect across various subgroups, analyses will be performed on the primary efficacy endpoint (defined in Section 3.2.1.2) across the following subgroups (categories with fewer than 5 participants may be combined with other categories):

- Race (White, Black or African American, Asian, Other)
- Age group (<65,  $\geq 65$  years)
- Sex (Male, Female)
- ECOG PS at baseline (0, 1)
- PD-L1 expression (<1%, ≥1%; <5%, ≥5%)

- Circulating CEA at baseline (<100,  $\ge100 \mu g/L$ ; <80,  $\ge80 \mu g/L$  and <50,  $\ge50 \mu g/L$ )
- Prior ICI treatment administration (Sequential, Combination with chemotherapy, no ICI)
- Time from initial diagnosis (<12 months,  $\geq$ 12 months)
- Number of organs involved (excluding primary tumor location) ( $<3, \geq 3$ )
- Tumor burden at baseline, ie, sum of the longest diameters of the target lesions (<100 mm,  $\geq$ 100 mm)
- Primary tumor (Gastric, GEJ)
- Previous treatment (doublet [FOLFOX or XELOX], triplet [other Chemotherapy+FOLFOX or other Chemotherapy+XELOX])
- Histology types (Intestinal, Diffuse, Mixed, Other)
- Peritoneal metastases (Yes, No)
- Previous gastrectomy (Partial, Total, No)
- Presence of ascites (Yes, No)
- Time to PD on first-line: <6 months;  $\geq 6$  months
- Region (Europe, East Asia, Other region)
- Prior treatment with a HER2 therapy (Yes, No)

If a sufficient number of responses is observed tables/plots will be provided, otherwise subgroup information will be displayed in listings only. For tables, objective response rate estimate and the corresponding 95% CI will be provided for each subgroup using the same method as applied to the primary analysis. Forest plots will be provided.

# 3.8 INTERIM ANALYSES

No formal interim analysis is planned in this study.

The study analysis will be conducted in 2 steps.

The first analysis step will be conducted when all evaluable treated participants have had at least 2 postbaseline tumor assessments, experienced confirmed objective response, or have discontinued the study for any reason. This study cut-off will occur approximatively 16 weeks after the date of the first IMP administration of the last participant: 12 weeks for 2 tumor assessment, and 4 weeks if a confirmation of response is needed.

The second analysis step will be based on the study cut-off date for analysis of the secondary efficacy endpoints, which include DOR and PFS, 4 months after the study cut-off date for the primary analysis. At that time, the primary analysis of ORR and DCR will also be updated.

The final analysis will be conducted at the end of the study. Only safety analyses will be updated at this time.

For each analysis step, the analysis cut-off date will be defined as the date of the database extraction that will be performed for the analysis after the cut-off (study cut-off for the first analysis step and second analysis step).

Analyses methods and conventions described in the other sections of this SAP will be applied for all analyses if applicable. The following additional rules will apply at the first analysis step and second analysis step:

- Participants without end of treatment status performed at the time of the analysis cut-off date will be considered as ongoing. Therefore:
  - Participants who did not discontinue the study intervention at the analysis cut-off date will be analyzed as "ongoing" in the disposition summary.
  - Their TE period and concomitant medication period will end at the analysis cut-off date.

# 4 SAMPLE SIZE DETERMINATION

The safety run-in (Part 1) aims to confirm the recommended dose of tusamitamab ravtansine loading dose Q2W in combination with ramucirumab according to DLTs observed.

Part 2 of this study is designed to obtain preliminary efficacy, safety, and PK data on tusamitamab ravtansine loading dose Q2W administered in combination with ramucirumab to participants with gastric or GEJ adenocarcinoma. As Part 2 is not intended to explicitly test a hypothesis, calculations of power and Type I error were not considered in the study design.

Assuming a prescreening failure rate of 70% and a study screen failure rate of 20%, approximatively 158 participants will be prescreened to achieve up to approximatively 38 treated participants in the safety run-in (Part 1) and Part 2.

# Sample size for the safety run-in (Part 1):

The actual sample size is expected to vary depending on DLTs observed. It is anticipated that around 6 to 12 DLT-evaluable participants will be enrolled in the safety run-in part of the study.

# Sample size for Part 2:

The initial plan is to treat a total of 32 participants evaluable for activity (at least 1 postbaseline evaluable tumor assessment, early clinical progression, or death due to disease progression). The 6 participants treated at the recommended DL in the safety run-in part will also be evaluable for the second part of the study.

Estimated ORR and 95% exact CIs by number of responders from a sample size of 32 evaluable participants for activity are listed in Table 10:

Table 10 - Estimated objective response rate (ORR) depending on number of responders

Abbreviation: CI = confidence interval

# 5 SUPPORTING DOCUMENTATION

## 5.1 APPENDIX 1 LIST OF ABBREVIATIONS

ADI:	actual dose intensity
AEs:	adverse events
AESI:	adverse event of special interest
ALP:	alkaline phosphatase
ALT:	alanine aminotransferase
AST:	aspartate aminotransferase
ATA:	antitherapeutic antibody
BCVA:	best corrected visual acuity
BOR:	best overall response
BUN:	blood urea nitrogen
CEA:	carcinoembryonic antigen
CEACAM5:	carcinoembryonic antigen related cell adhesion molecule 5
cfDNA:	circulating-free deoxyribonucleic acid
CI:	confidence interval
CMQ:	company MedDRA queries
COVID-19:	coronavirus disease 2019
CR:	complete response
CTCAE:	common terminology criteria for adverse events
DCR:	disease control rate
DL:	dose level
DLT:	dose-limiting toxicity
DOR:	duration of response
ECG:	electrocardiogram
ECOG:	Eastern Cooperative Oncology Group
eGFR:	estimated glomerular filtration rate
EOT:	end of treatment
GEJ:	gastroesphageal junction
HLGT:	high level group term
HLT:	high-level term
IHC:	ImmunoHistoChemistry
IMP:	investigational medicinal product
INR:	international normalized ratio
IRT:	interactive response technology
ITT:	intent-to-treat
LDH:	lactate dehydrogenase
LLN:	lower limit of normal
LLOQ:	lower limit of quantification
LLT:	lower-level term
MDRD:	modification of diet in renal disease
MedDRA:	Medical Dictionary for Regulatory Activities

Statistical Analysis Plan SAR408701-ACT16444 - tusamitamab ravtansine 17-Jul-2023 Version number: 1

NCI	National Cancer Institute
ODD.	national Calleer Institute
UKK:	objective response rate
PCSA:	potentially clinically significant abnormalities
PD:	progressive disease
PDI:	planned dose intensity
PFS:	progression-free survival
PK:	pharmacokinetic
PR:	partial response
PS:	performance status
PT:	preferred term
RD:	recommended dose
RDI:	relative dose intensity
RECIST:	response evaluation criteria in solid tumors
SAEs:	serious adverse events
SAP:	statistical analysis plan
SD:	stable disease
SOC:	system organ class
TE:	treatment-emergent
TEAE:	treatment-emergent adverse event
ULN:	upper limit of normal
ULOQ:	upper limit of quantification
WHO-DD:	World Health Organization-drug dictionary

# 5.2 APPENDIX 2 PARTICIPANT DISPOSITIONS

The number (%) of participants included in each of the analysis populations listed in Table 4 will be summarized. Reasons for exclusion from the population without trial impact (disruption) due to COVID-19 will be summarized.

Prescreen failures are defined as participants who consent to participate in the prescreening phase of the study but are not subsequently screened. The number (%) of prescreen failures and reasons for prescreen failures will be provided in the prescreened population.

Screen failures are defined as participants who consent to participate in the study but are not subsequently enrolled. The number (%) of screen failures and reasons for screen failures will be provided in the screened population.

Regarding intervention discontinuation, the following definitions will be used:

- Permanent **partial** intervention discontinuation is defined as the discontinuation of at least one of the study drugs but at least one is continued
- Permanent **full** intervention discontinuation is defined as the discontinuation of all the study drugs

The number (%) of participants in the following categories will be provided:

- Enrolled participants
- Enrolled but not treated participants
- Enrolled and treated participants
- Participants still on study intervention
- Participants who discontinued the study intervention, and main reason for permanent full study intervention discontinuation
- Participants who discontinued the study intervention, and main reason for permanent partial discontinuation of tusamitamab ravtansine
- Participants who discontinued the study intervention, and main reason for permanent partial discontinuation of ramucirumab
- Participants who discontinued the study, and main reason for study discontinuation

Reasons for permanent full/partial study intervention and study discontinuation such as "adverse event" and "other reasons" will be split as related versus not related to COVID-19 (if applicable).

Any treated and not enrolled participants will also be listed.

In addition, the number (%) of participants pre-screened, pre-screened failed, screened, screened-failed, enrolled and treated, with permanent full intervention discontinuation and with early study discontinuation will be provided by country and site.

For all categories of participants (except for prescreened, screened, and nonenrolled categories), the percentage will be calculated using the number of participants in the all-treated population as the denominator.

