# 2 ANALYSIS POPULATIONS

The following populations for analyses are defined:

Population	Description		
Prescreened	All participants who signed the prescreening informed consent for CEACAM5 assessment of their biopsy.		
Screened	All participants who signed the screening informed consent for study participation.		
Enrolled	Participants from screened population who have been allocated to intervention regardless of whether the intervention was received or not.		
All-treated	All enrolled participants exposed to the study treatment, regardless of the amount of treatment administered. All safety analyses will be performed on this population, which is also the primary population for analysis of all efficacy parameters.		
DLT-evaluable (Part 1)	All enrolled participants who received 2 cycles with at least 80% of the intended dose for both tusamitamab ravtansine and ramucirumab at each of the first 2 infusions. Any participant who experienced a DLT during that period will also be DLT-evaluable.		
Activity	All-treated participants who have measurable disease at study entry and at least 1 postbaseline evaluable tumor assessment. Participants with no postbaseline evaluable tumor assessment but with an early clinical progression or who died from disease progression will also be included in this set. This population is the secondary population for analysis of efficacy parameters.		
Pharmacokinetic (PK)	All participants from the all-treated population with at least 1 postbaseline PK concentration (whatever the cycle and even if dosing is incomplete) with adequate documentation of dosing and sampling dates and times.		
ATA	All participants from the all-treated population with at least 1 postbaseline ATA result (negative, positive, or inconclusive).		
Population without trial impact	All treated participants:		
(disruption) due to COVID-19	
 
without any critical or major deviation related to COVID-19
 
		
	
 
and who did not permanently discontinue treatment due to COVID-19
 
		
	
 
and who did not permanently discontinue study due to COVID-19.
 
		

Table 4 - Populations	for analyses
-----------------------	--------------

In practice, a participant will be included in the enrolled population if the question "Will the subject continue in the treatment phase?" has been answered "Yes" in the "Completion of screening phase" e-CRF page.

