# 3.6.1 Extent of exposure

#### 3.6.1.1 Overall exposure

The dose information will be assessed by the following variables:

- Overall number of cycles started, defined by the number of cycles in which at least one dose of any study interventions is administered.
- Duration of overall exposure (in weeks) is defined as (Last day of exposure first day of exposure +1)/7.
  - The first day of exposure is defined as the first administration date with non-zero dose for at least one of the IMP (tusamitamab ravtansine or ramucirumab).
  - The last day of exposure is the day before the theoretical date of the next administration (after the last administration), defined as the last administration date of at least one IMP + 14 days 1 (tusamitamab ravtansine and ramucirumab).

The total number of cycles started, and the number of cycles started by participants will be summarized as a quantitative variable and by category (number (%) of participants receiving at least 1 cycle, at least 2 cycles, etc). The duration of overall exposure will be summarized quantitatively.

The following variable will be computed to describe overall dose modification (cycle delay):

• Cycle delay: A cycle is deemed as delayed if the start date of the current cycle – 14 days – start date of the previous cycle is >2 days. Cycle delay is not defined for the first cycle.

Cycle delay will be analyzed at the participant (with number of participants used as denominator) and cycle (with number of cycles used as denominator) levels, as follows:

- Number (%) of participants with a least 1 cycle delayed
  - Number (%) of participants with a cycle delayed between 3 and 7 days (using maximum delay across all cycles)
  - Number (%) of participants with a cycle delayed between 8 and 14 days (using maximum delay across all cycles)
  - Number (%) of participants with a cycle delayed >14 days (using maximum delay across all cycles)
- Number (%) of cycles delayed
  - Number (%) of cycles delayed between 3 and 7 days
  - Number (%) of cycles delayed between 8 and 14 days
  - Number (%) of cycles delayed >14 days

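### SAP disposition rows for enrolled participants are divided by the all-treated population, which excludes anyone enrolled but undosed; the overall cycle-delay rate has a smaller mismatch of the same kind

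*SAP*

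**What the plan says.** **Disposition.** SAP section 5.2 asks for a number and percentage for a list of categories that includes all enrolled participants, "Enrolled but not treated participants", and those both enrolled and treated. A single denominator rule follows the list: "the percentage will be calculated using the number of participants in the all-treated population as the denominator". The only exemptions are given in a parenthesis: "except for prescreened, screened, and nonenrolled categories".

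SAP section 2 defines the two populations involved. Enrolled means "Participants from screened population who have been allocated to intervention regardless of whether the intervention was received or not". All-treated means "All enrolled participants exposed to the study treatment, regardless of the amount of treatment administered". In practice enrolment is read from the answer on the screening-completion eCRF page about continuing into the treatment phase, so it does not depend on a dose having been given.

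**Cycle delay.** SAP section 3.6.1.1 states: "Cycle delay is not defined for the first cycle". Delay is then to be analysed at the participant level and at the "cycle (with number of cycles used as denominator) levels". Nothing removes first cycles from that count. Sections 3.6.1.2 and 3.6.1.3 take the same approach for each drug's dose delay, with cycles started as the denominator.

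**The concern.** A percentage is readable when the people or cycles in the numerator belong to the denominator and the denominator holds only units that could have the event. Each of these two rules fails one half of that test.

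In the disposition table, participants who were enrolled but not treated lie wholly outside the all-treated population. Their percentage is a ratio of two disjoint groups, and the enrolled row is a whole divided by its own part. The enrolled-and-treated row is 100% by construction and carries no information.

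In the exposure table, a first cycle can never count as delayed but always adds to the denominator, so the cycle-level rate is pulled down. The pull is strongest when participants receive few cycles. Delay is one of the protocol's listed responses to keratopathy, neuropathy and neutropenia, so it is a figure that readers of the safety section will look at.

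**Working it through.** **The one related count in the plan.** SAP section 4 and protocol section 9.1 expect about 158 prescreened participants to give up to about 38 treated, with 70% prescreening failure and 20% screening failure. Check: 38 / (0.30 × 0.80) = 38 / 0.24 = 158.3, which reproduces 158. In reverse, 158 × 0.24 = 37.9. The plan therefore makes no allowance for people who pass screening and are then not dosed. The number enrolled but untreated has to be assumed.

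**Disposition.** Inputs: T = 32 or 38 treated (SAP section 1.1); u = number enrolled but untreated, assumed 0 to 4.

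- Enrolled row as written: 100 × (T + u) / T
- Enrolled-but-untreated row as written: 100 × u / T
- The same row over the enrolled population: 100 × u / (T + u)

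| T | u | Enrolled, as written | Untreated, as written | Untreated, over enrolled |
|---|---|---|---|---|
| 32 | 0 | 100% | 0% | 0% |
| 32 | 1 | 33/32 = 103.1% | 1/32 = 3.1% | 1/33 = 3.0% |
| 32 | 4 | 36/32 = 112.5% | 4/32 = 12.5% | 4/36 = 11.1% |
| 38 | 0 | 100% | 0% | 0% |
| 38 | 1 | 39/38 = 102.6% | 1/38 = 2.6% | 1/39 = 2.6% |
| 38 | 4 | 42/38 = 110.5% | 4/38 = 10.5% | 4/42 = 9.5% |

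With the enrolled population as denominator, the enrolled row is 100% and the treated and untreated rows add up to it. With 38 treated and 2 untreated, for example, 38/40 = 95.0% and 2/40 = 5.0%.

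**Overall cycle delay.** Let N participants start m cycles each on average. Cycles started number N × m. Each participant has exactly one first cycle, so cycles at risk of delay number N × (m − 1). The reported rate is therefore (m − 1)/m of the rate among cycles at risk, and its ceiling is 100 × (m − 1)/m.

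Inputs: 14-day cycles and a median of 18 weeks on treatment (SAP section 1.1) give 18/2 = 9 cycles. The formula needs a mean, which the documents do not give, so the median stands in for it. The 20% rate and m = 3 are assumptions for illustration.

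- m = 9: ceiling 88.9%; 20% × 8/9 = 17.8%
- m = 3: ceiling 66.7%; 20% × 2/3 = 13.3%

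To recover the at-risk rate, multiply the reported rate by m/(m − 1): 1.125 at m = 9 and 1.5 at m = 3.

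**The case against.** On disposition, the best reply is that the problem may never arise. It needs at least one enrolled participant with no dose, and SAP section 2 counts people of unclear exposure as treated, which makes such cases fewer. Counts are printed beside each percentage, so a reader would see what had happened. No analysis uses these percentages. All of this stands and keeps the point small. It does not rescue the rule: the SAP provides a row for undosed enrollees, and the rule cannot give that row a valid percentage.

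On delay, the reply is stronger. The share of all cycles that were delayed is a legitimate descriptive quantity, and its denominator is stated openly. The at-risk rate can be recovered, because section 3.6.1.1 also tabulates total cycles started, and subtracting the number of participants treated gives the cycles at risk. Delay also shows in relative dose intensity, in the tables of adverse events leading to dose modification, and in the corneal event overview.

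A reader might go further and infer that the participant-level percentages and the per-drug dose-delay rows are wrong too. The documents do not support that. A participant who received one cycle had no delay, so a percentage of treated participants is sound. Per drug, delay, reduction and omission are sub-rows of one dose-modification row and share its denominator, and moving delay alone would break that structure. Cycles from Cycle 2 onward would not be the exact at-risk set there either, because per-drug delay compares administration dates in successive cycles and an omitted dose leaves no such comparison.

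**Conclusion.** The disposition rule is wrong as written, with a conditional effect. With 1 to 4 undosed enrollees (an assumption), the enrolled row would read 103.1% to 112.5% at 32 treated or 102.6% to 110.5% at 38, and the untreated row would be a share of a group containing none of those participants. With none undosed, every printed figure is correct. It would be a mistake to say that the table will exceed 100%; the documents show only that it can.

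The delay point is secondary. It is a mild attenuation of one stand-alone rate, about 2.2 percentage points (20.0 − 17.8) for an assumed 20% at 9 cycles, and more if treatment is short. A reader might take it as evidence that toxicity is being hidden. The other delay outputs in the SAP, and the fact that the at-risk rate can be recovered, argue against that reading.

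Response rate, disease control, duration of response, progression-free survival, DLT incidence and sample size are all unaffected.

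**What to change.** In SAP section 5.2, use the enrolled population as denominator for the enrolled, enrolled-but-not-treated and enrolled-and-treated rows. Keep all-treated for the remaining categories to which it now applies.

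In section 3.6.1.1, use cycles from Cycle 2 onward as denominator for the overall percentage of cycles delayed, together with its bands by length of delay.

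Leave the participant-level percentages and the per-drug dose-modification rows on their stated denominators. Add a footnote that the first cycle is included although delay is undefined there.

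The cost is a few words in the SAP and the matching program denominators. No new data are needed. The overall cycle-delay percentage will be somewhat higher.

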#### Protocol deviations

Critical and major protocol deviations (automatic or manual) will be summarized in the all-treated population, as well as displayed separately as related or not related to COVID-19 (if applicable).

# 5.3 APPENDIX 3 DEMOGRAPHICS AND BASELINE CHARACTERISTICS, PRIOR OR CONCOMITANT MEDICATIONS

#### Demographics, baseline characteristics, medical surgical history

The following demographics and baseline characteristics, medical and surgical history and disease characteristics at baseline will be summarized using descriptive statistics in the all-treated population.

Demographic and baseline characteristics

- Age in years as quantitative variable and in categories (<65, 65 to  $<75, \ge 75$ )
- Sex (Male, Female)

- Race (American Indian or Alaska Native, Asian, Black or African American, Native Hawaiian or Other Pacific Islander, White, Not reported, Unknown)
- Ethnicity (Hispanic or Latino, Not Hispanic or Latino, Not reported, Unknown)
- Region (Europe [Belgium, Russian and Spain], East Asia [Japan, Korea], other region [Turkey])
- ECOG PS (0,1)
- Weight in kg as a quantitative variable
- BSA in m^2 as a quantitative variable

Baseline safety and efficacy parameters (apart from those listed above) will be presented along with the safety and efficacy summaries.

Medical (or surgical) history includes relevant history of previous pathologies and surgeries. Medical and surgical history will be coded to a LLT, PT, HLT, HLGT, and associated primary SOC using the MedDRA version currently in effect at Sanofi at the time of database lock.

Specific disease history includes primary tumor site (gastric, GEJ), histopathology type, staging, Siewert-Stein classification, histology type, time from initial diagnosis to first administration of IMP (in months).

Specific disease status at study entry includes extend of diseases, number (both excluding and including primary tumor location) and type of organs involved (including primary tumor location), ascites presence, PD-L1 expression (<1%,  $\ge1\%$  and <5%,  $\ge5\%$ ), Peritoneal metastases (Yes, No).

CEACAM5 expression, circulating CEA (<100  $\mu$ g/L, ≥100  $\mu$ g/L, <80  $\mu$ g/L, ≥80  $\mu$ g/L, <50  $\mu$ g/L, ≥50  $\mu$ g/L, <5  $\mu$ g/L, ≥5  $\mu$ g/L and <3  $\mu$ g/L, ≥3  $\mu$ g/L) and type of tumor biopsy (archival /fresh) will also be described.

